1. PURPOSE OF THE STUDY

a. Brief Summary

This study aims to test the effectiveness of a Type 2 Diabetes (T2D) prevention program for individuals who have been diagnosed with prediabetes compared to a T2D educational control group. Project Health is an obesity prevention program and has produced a 42% to 53% reduction in future onset of overweight/obesity and also produced greater reductions in negative affect compared to assessment-only controls that persisted. Project Health has been adapted to prevent onset of T2D among individuals with prediabetes. The study aims to test the effectiveness of Project Health at reducing BMI, HbA1c levels, increase physical activity and improve glucose control.

b. Objectives

Aim 1 is to test the hypothesis that participants who complete the T2D Project Health will show significantly greater reductions in BMI and HbA1c, the primary outcomes, by 3-month follow-up than participants randomized to the T2D education video control condition.

Aim 2 is to test the hypothesis that participants who complete the T2D Project Health will show significantly greater reductions in self-reported caloric intake and greater increases in physical activity by 3-month follow-up than participants randomized to the T2D education video control condition.

If this pilot and feasibility trial provides evidence that Project Health significantly reduces weight gain and improves glucose control, we plan on conducting a fully-power trial that will test whether this brief, cost effective prevention program significantly reduces future onset of T2D among individuals with impaired glucose control. As such, this represents a translational study on the prevention of T2D.

c. Rationale for Research in Humans

The purpose of this study is to test the effectiveness of a Type 2 Diabetes prevention program, adapted Project Health. This study must use humans due to the nature of the educational aspect because the programs require speech as a method of communication.

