We will use a random number generator to determine if participants will be in Project Health or the educational control. If an even number is generated, the participant will be assigned Project Health. If an odd number is generated, the participant will be assigned to educational control. As there is a 50% chance the number will be either even or odd, there is a 50% chance that someone will be assigned either to Project Health or the educational control. It is only after the baseline assessment that individuals will be randomized. This will prevent the assessor at baseline from being influenced by which group the participant will be in. The assessor completing the assessments at post-test and 3-month follow-up will be blind to the participant's condition.

Project Health:

Project Health will be delivered in six 1-hour group sessions that will be held weekly. In addition, participants will be asked to complete 30 mins of response inhibition and attention trainings once per week between the sessions. This program promotes to retain the gradual lifestyle modification designed to bring energy intake into balance with energy output and the food response inhibition and attention training, but will adapt the dissonance-induction activities to focus on the negative

effects of developing T2D in addition to the negative effects of obesity, overeating, and a sedentary lifestyle.

Participants who are assigned to the Project Health condition will receive reminders and writing prompts via a secure text messaging platform, TextMagic. The text reminders will be used to remind participants to complete the writing prompts and one computer task between group sessions. This computer task is a choice of one game that the participants had played during their intervention group. The writing prompts being used will help to reinforce the response inhibition and attention trainings. No personal participant information will be shared or asked for via TextMagic.

Educational Control:

We selected a T2D management psychoeducational comparison condition. To match Project Health, the educational videos will be delivered in 6 1-hour blocks. The educational group will be instructed to watch videos on nutrition, exercise, and how to maintain general health during the lifespan

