If participants are randomized to Project Health, they will meet in groups of 6 individuals led by clinician. Groups will meet once a week in-person for an hour, for six weeks. Each week involves homework that participants are asked to complete before the next session. If participants are assigned to the Education intervention, they will be asked to watch one-hour of videos including information about T2D each week for six weeks.

Post-Test:

After the six weeks of either Project Health or the educational control, participants will be asked to complete the same assessments that they did at baseline, but not the blood tests.

3-Month Follow-up:

At 3-month follow-up, participants will again complete the assessments. After the 3-month follow-up, participants have completed all study responsibilities.

1-Year Follow-Up:

We propose to collect A1c data over 1 year follow up

First we will check to see in Epic if the participant is a Stanford patient.

If they haven't had a recent test or not in Stanford system we will ask if they would be willing to send any recent A1c blood test results.

If no to both, the participant will be offered to have an HbA1c kit sent to them to do a finger prick at home. The participant will send the kit to the research lab in Minnesota to be processed. Kits come with already pre-paid shipping labels that are addressed only to the Minnesota lab, no return address or any PHI from the participant is included. The participant will be offered a \$10 Amazon gift card for completing and shipping the HbA1c kit.

b. Procedure Risks

These research procedures provide minimal risk to subjects. We are using current and empirically evaluated measures and research staff available who have been fully trained both in administrating physiological interviews. Project Health has also been tested in

multiple trials and has produced only positive effects, there has been no history of symptoms worsening as a result of participating in the program.

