Evaluating a Type 2 Diabetes Prevention Program

NCT: 5822648

04/16/2023

**Analyses.** For the continuous response variables in Aims 1 and 2 we will fit linear mixed effects models (LME) or generalized additive models (GAM) if change across the study is nonlinear. All models will include an interaction of time since the start of the study (in months) and condition (as well as all lower-order main effects). For both LMEs and GAMs, we will control for the lack of independence between the observations within a participant by including random intercepts and random slopes (if necessary) for the participants in our models and for participants nested within groups.

To detect for differences in the onset of T2D (Aim 1) between the intervention and control condition, we will fit a Cox proportional hazard model using the survival package (Therneau, 2022) in R. The proportional hazard assumption will be assessed and in the event of violations of this assumption, stratified proportional hazard models will be fit.

For the mediation analysis for Aim 2, the mediation package (Tingley et al., 2014) in R will be used to employ the causal mediation approach described in Imai et al. (2010). This is a more general and flexible causal mediation framework than the traditional structural equation modeling approach to mediation. Specifically, this approach enables (1) definitions of causal mediation effects that are independent of a particular statistical model, (2) specification of the identifiability assumption, and (3) a framework that can be applied to a myriad of models (most importantly for this study, LMEs, GAMs, and survival models). In addition, sensitivity analyses can be conducted to explore the sequential ignorability assumption. Using this framework involves modeling the onset of T2D via a parametric survival regression model that includes condition and the proposed mediator (percent body fat). This model's output is then combined with the mediator model's output, the percent body fat model from Aim 1, and used to calculate the average causal mediation effect (ACME), the proportion of the total effect that is mediated as well as other mediation statistics, which can then be tested using either quasi-Bayesian Monte Carlo or the non-parametric bootstrap.

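### Aims 1 and 2 are worded as Project Health completers against all randomised controls, and the SAP names no analysis set to settle who is compared

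*Protocol*

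**What the plan says.** Protocol section 1b (Objectives) is the only place where the primary comparison is stated. Aim 1 predicts that "participants who complete the T2D Project Health will show significantly greater reductions in BMI and HbA1c, the primary outcomes", by the 3-month follow-up "than participants randomized to the T2D education video control condition". Aim 2 has the same form: "participants who complete the T2D Project Health will show significantly greater reductions in self-reported caloric intake", with a matching claim for physical activity, again against participants randomised to control.

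The SAP gives the model for these outcomes: "All models will include an interaction of time since the start of the study (in months) and condition". It does not say who enters the model. Neither document mentions intention-to-treat, per-protocol or completer sets, and neither says how people who stop attending are handled.

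Completion is not defined either. Besides six weekly group sessions, section 2a says that "participants will be asked to complete 30 mins of response inhibition and attention trainings once per week between the sessions", and that "Each week involves homework that participants are asked to complete before the next session". A completer could be defined by any of these or by a combination.

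Section 2b allows a participant to leave the intervention, the study, or both at any time. The plan therefore foresees people who stop the program but remain available for assessment.

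**The concern.** Randomisation makes the two arms comparable in expectation. Keeping only completers in one arm and everyone in the other removes that protection. People who finish a six-week behavioural program may differ in motivation, health or circumstances from those who do not, and those differences may affect BMI and HbA1c whatever the program does. The control arm still contains the people who would not have completed.

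If completers would have done better anyway, the comparison favours Project Health; if worse, it counts against it. There is no bias if everyone completes or if completion is unrelated to outcome. The documents do not say which case applies.

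Two decisions depend on a significant result: going on to a fully powered trial (section 1b) and offering the program to controls (section 2f). With neither the analysis set nor completion fixed in advance, both could be chosen after the data are seen.

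**Working it through.** **Text side by side**

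| Place | Project Health side | Control side |
|---|---|---|
| Protocol 1b, Aims 1 and 2 | those who complete | those randomised |
| Protocol 2a | condition means the assigned arm | as assigned |
| Protocol 10 | intervention participants, no completion filter | control participants |
| SAP, mixed models | condition, set not stated | condition, set not stated |

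Section 2a supports the assigned-arm reading of condition: "Participants who are assigned to the Project Health condition will receive reminders and writing prompts". That reading contradicts the aims as written, and nothing in the SAP resolves the conflict. The SAP's Cox model for diabetes onset also compares groups "between the intervention and control condition". That shows only that no set is named there either, because onset is not an outcome in the protocol's two aims.

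**Size, as an illustration.** The plan has no figure to reproduce: 62 participants (section 8a) are given without alpha, power, effect size, SD or dropout.

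Inputs:
- From the protocol: 62 participants and a 50% allocation chance, so 31 per arm in expectation.
- Assumed: no true effect; a two-sided pooled t-test of change at 0.05 (2.5% in each direction); completion probability p, the same in both arms; SD 1 within completers and within non-completers; non-completers worse by a gap g.

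The completer mean exceeds the mean of all controls by

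bias = (1 − p) × g.

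For p = 0.8 and g = 0.5 this is 0.2 × 0.5 = 0.10 SD.

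Simulated rate of falsely finding Project Health better (200,000 trials per scenario):

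| Analysis | Gap g | p = 0.9 | p = 0.8 | p = 0.6 |
|---|---|---|---|---|
| Completers vs all controls: bias (SD) | 0.5 | 0.05 | 0.10 | 0.20 |
| Completers vs all controls: false better | 0.5 | 3.75% | 5.39% | 9.29% |
| Completers vs all controls: bias (SD) | 1.0 | 0.10 | 0.20 | 0.40 |
| Completers vs all controls: false better | 1.0 | 5.42% | 9.98% | 22.87% |
| Completers vs all controls: false better | −0.5 (non-completers better) | 1.60% | 0.98% | 0.42% |
| Completers vs all controls: false worse | −0.5 (non-completers better) | 3.74% | 5.44% | 9.42% |
| All randomised as assigned, complete outcomes: false better | all of the above | 2.4–2.6% | 2.4–2.6% | 2.4–2.6% |

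With g = 0 or p = 1 the completer comparison also stays at 2.5%.

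Hand check at p = 0.8, g = 0.5:
- About 0.8 × 31 = 24.8 completers; control variance 1 + 0.8 × 0.2 × 0.5² = 1.04.
- Pooled variance (23.8 × 1 + 30 × 1.04)/53.8 = 1.022; pooled SE √[1.022 × (1/24.8 + 1/31)] = 0.272; critical difference about 2.005 × 0.272 = 0.546.
- True SE √(1/24.8 + 1.04/31) = 0.272. Then (0.546 − 0.10)/0.272 = 1.64, a tail area of about 5%, close to the simulated value.

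**Dropout that rewording does not cure.** Suppose half of the Project Health non-completers leave without outcome data and no controls do. Non-completers are then (1 − p)/(1 + p) of the observed Project Health arm, so the assigned-arm bias is

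[(1 − p) − (1 − p)/(1 + p)] × g = p(1 − p)g/(1 + p).

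For p = 0.8 and g = 0.5 this is 0.8 × 0.2 × 0.5/1.8 = 0.044 SD. The simulated rates at p = 0.9/0.8/0.6 are 3.05/3.59/4.46% (g = 0.5) and 3.64/4.89/7.18% (g = 1.0). If the same loss rule applies in both arms, the rate is 2.5%.

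**Does the t-test stand in for the SAP model?** With HbA1c at baseline and 3 months only, as section 2a has it, the random-intercept time-by-condition test is the t-test of change. With three visits (assumed at 0, 1.5 and 4.5 months), comparing within-person slopes gave 3.8/5.5/9.7% for g = 0.5 and 5.6/10.4/23.7% for g = 1.0. Group nesting was ignored.

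**A different selection model.** Let completion depend on a latent tendency with correlation ρ to improvement. For ρ from 0.2 to 0.5 and completion from 90% down to 60%, the spurious benefit ran from 0.04 to 0.32 SD and the two-sided error from 5.3% to 19.1%. With ρ = 0 the error was about 5%.

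For scale, 31 per arm has 80% power for a difference of about (1.96 + 0.842) × √(2/31) = 0.71 SD.

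**The case against.** The strongest reply is that the aims are loosely drafted. They state hypotheses and do not define a population. The SAP is where the analysis is specified, and it uses condition, which sections 2a and 10 suggest means the assigned arm. On that view no completer analysis is planned and the error rates above describe something nobody will run. That may be so, and it is why the point is put as an unresolved conflict and not as a demonstrated flaw in the analysis. It does not remove the need for a change: if assigned arm is meant, the aims contradict it; if not, the primary comparison is open to selection bias.

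The magnitudes are also assumed. The 23% figure needs both 40% non-completion and a full 1.0 SD gap, and nothing in the documents supports either; at 90% completion and a 0.5 SD gap the rate is 3.75%. This stands.

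The gain from the fix is also smaller than the headline contrast when dropout is one-sided: at 80% completion and a 0.5 SD gap, 3.59% against 5.39%, a difference of 1.8 points. This stands too; missing outcome data are a separate problem.

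Finally, this is a pilot, and a false positive would be tested again in the full trial. That lowers the stakes, but the decision to go on is itself tied to significance.

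**Conclusion.** The concern holds and should be fixed. The primary hypothesis, as written, compares a group selected after randomisation with an unselected one. It conflicts with the natural reading of the SAP, and no stated analysis set or definition of completion settles the matter. If the aim is followed literally, the bias is (1 − p) × g and can go either way. Over the assumed ranges (60–90% completion, gap 0.5–1.0 SD) the false-better rate is about 4% to 23% against 2.5%, and it drops below 2.5% if non-completers have the better prognosis. These figures illustrate the risk and are not predictions. Confidence is medium, because loose drafting is a real possibility.

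**What to change.** - Reword both aims so that the Project Health side, like the control side, is everyone randomised to it.
- State in the SAP that the primary analysis includes all randomised participants in their assigned arm, using every available visit regardless of sessions attended.
- Label any completer analysis supplementary, and define completion in advance by sessions, trainings, homework or a stated combination.

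The cost is a few sentences in the protocol aims and the SAP, with no change to eligibility, visits or sample size. There are two downsides. The estimated effect may be smaller, because non-attenders count. The rewording also does not by itself remove bias from people who leave without outcome data, so the SAP should state how missing outcomes are handled.

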2. STUDY PROCEDURES

a. Procedures

Participants will be recruited through flyers, online postings, and other postings at various clinics in the Bay Area. To determine eligibility, during screening participants will be asked their age, gender.

On the flyers and other recruitment materials, participants will be directed to a short survey on a secure platform that only asks for contact information to show interest in the study. The study team will use the contact information provided to set-up a phone screen for interested individuals. If the participant shows interest through one of the Honest Broker methods (such as MyChart) or through ResearchMatch.org which shares the contact information with the research team, then a member of the research team will reach out to the individual using the contact information provided to thank them for their interest and schedule a phone screen. See section 13 for the phone screen.

After the participant completes the phone screen, a member of the study team will contact them to confirm eligibility. Consent (for ages 18- 65) will be secured prior to enrollment.

Baseline Assessment:

After eligibility is confirmed but before groups begin, the participant will come in for their baseline assessment. At baseline, participants will complete the Paffenbarger Activity Questionnaire to assess physical activity, the Beck Depression Inventory, and the Eating Disorder Diagnostic Scale. We will also have participants get an HbA1c test and fasting glucose test through the Stanford CTRU. Finally, participants will complete a Bod Pod Assessment, measuring Body Fat. Prior to the start of groups, participants will complete the Automated Self-Administered 24-hr Dietary Recall (ASA-24) to assess dietary intake on 2 weekdays and 1 weekend.

Prevention program:

After baseline assessments are completed, participants will be randomized to either the Project Health groups or the educational control.

Randomization:

We will use a random number generator to determine if participants will be in Project Health or the educational control. If an even number is generated, the participant will be assigned Project Health. If an odd number is generated, the participant will be assigned to educational control. As there is a 50% chance the number will be either even or odd, there is a 50% chance that someone will be assigned either to Project Health or the educational control. It is only after the baseline assessment that individuals will be randomized. This will prevent the assessor at baseline from being influenced by which group the participant will be in. The assessor completing the assessments at post-test and 3-month follow-up will be blind to the participant's condition.

Project Health:

Project Health will be delivered in six 1-hour group sessions that will be held weekly. In addition, participants will be asked to complete 30 mins of response inhibition and attention trainings once per week between the sessions. This program promotes to retain the gradual lifestyle modification designed to bring energy intake into balance with energy output and the food response inhibition and attention training, but will adapt the dissonance-induction activities to focus on the negative

effects of developing T2D in addition to the negative effects of obesity, overeating, and a sedentary lifestyle.

Participants who are assigned to the Project Health condition will receive reminders and writing prompts via a secure text messaging platform, TextMagic. The text reminders will be used to remind participants to complete the writing prompts and one computer task between group sessions. This computer task is a choice of one game that the participants had played during their intervention group. The writing prompts being used will help to reinforce the response inhibition and attention trainings. No personal participant information will be shared or asked for via TextMagic.

Educational Control:

We selected a T2D management psychoeducational comparison condition. To match Project Health, the educational videos will be delivered in 6 1-hour blocks. The educational group will be instructed to watch videos on nutrition, exercise, and how to maintain general health during the lifespan

If participants are randomized to Project Health, they will meet in groups of 6 individuals led by clinician. Groups will meet once a week in-person for an hour, for six weeks. Each week involves homework that participants are asked to complete before the next session. If participants are assigned to the Education intervention, they will be asked to watch one-hour of videos including information about T2D each week for six weeks.

Post-Test:

After the six weeks of either Project Health or the educational control, participants will be asked to complete the same assessments that they did at baseline, but not the blood tests.

3-Month Follow-up:

At 3-month follow-up, participants will again complete the assessments. After the 3-month follow-up, participants have completed all study responsibilities.

1-Year Follow-Up:

We propose to collect A1c data over 1 year follow up

First we will check to see in Epic if the participant is a Stanford patient.

If they haven't had a recent test or not in Stanford system we will ask if they would be willing to send any recent A1c blood test results.

If no to both, the participant will be offered to have an HbA1c kit sent to them to do a finger prick at home. The participant will send the kit to the research lab in Minnesota to be processed. Kits come with already pre-paid shipping labels that are addressed only to the Minnesota lab, no return address or any PHI from the participant is included. The participant will be offered a \$10 Amazon gift card for completing and shipping the HbA1c kit.

b. Procedure Risks

These research procedures provide minimal risk to subjects. We are using current and empirically evaluated measures and research staff available who have been fully trained both in administrating physiological interviews. Project Health has also been tested in

multiple trials and has produced only positive effects, there has been no history of symptoms worsening as a result of participating in the program.

The above procedures present minimal risk. Engaging in the intervention modules carries minimal risk for emotional discomfort or stress. Subjects will have the option of not participating in conversations or exercises in the intervention modules that cause them any discomfort. They will also be free to withdraw from participating in the intervention and/or overall study at any time. Survey measures are non-invasive and present minimal risk. Using blood draws for A1c may be minimally invasive but provide no added level of risk or discomfort beyond routine diabetes management tasks.

c. Use of Deception in the Study

Deception will not be used.

d. Use of Audio and Video Recordings

Participants will be informed that we will make video recordings of Project Health groups for clinical supervision and quality assurance purposes. These recordings will be reviewed by the primary investigator to assess intervention fidelity and therapeutic competence of the group leaders. Email supervision based on these ratings will be provided to facilitators which has been found to maximize intervention effects. After they are viewed and rated for fidelity and competence, all records of the recordings will be deleted from devices and destroyed. Recordings are not optional. As the group sessions are in-person it is possible for someone to go out of view of the camera, but their voices will still be recorded. There are three main factors that increase cognitive dissonance: public accountability, level of effort, and voluntary basis. By recording the sessions, public accountability is greatly increased, and the effect of the intervention improves. Thus, if they are in Project Health individuals must be willing to be recorded.

e. Alternative Procedures or Courses of Treatment

There are not any programs designed to decrease risk of T2D.

f. Will it be possible to continue the more (most) appropriate therapy for the participant(s) after the conclusion of the study?

If Project Health produces significantly larger improvements than the educational lectures, we will offer the Project Health to educational controls.

g. Study Endpoint(s)

It is important to test whether effects persist at 3-month follow-up even if there are good effects at posttest, as it is possible that the effects may not persist. The effects of this brief prevention program typically have shown good persistence through 3- year follow-ups.

